## 15. DATA NOT SUMMARIZED OR PRESENTED

Any information not described will not appear in the interim analysis but may contribute to datasets that support the final study report.

Other data collected in eCRF, Interactive Voice Response System (IVRS) or any other clinical trial data collection system which is not described above will be presented in the appendix listings.

## APPENDIX 1. PROGRAMMING CONVENTIONS FOR OUTPUTS

### SHIRE OUTPUT STANDARDS – TFLS4SHIREFINALV6.0

Outputs will be presented according to Shire output standards document TFLS4ShireFinalV6.0.

General considerations which are applicable to the study are summarized as following:

- **STATISTICS PRESENTATION**

For the by-time-point tables, the number of subjects at each timepoint (n) represents the number that had a valid result for a given parameter at that timepoint.

The default summary statistics presented in the TFLS4Shire table shells for continuous variables include n, mean, standard deviation, median, minimum, and maximum. For categorical variables, the count (n) and percent (%) are the default statistics; unless otherwise stated or the associated number of subjects for the corresponding time point is provided, the denominator for percentages is N (the number of subjects in the treatment group/analysis set). Note that for any summary by subgroups (e.g., by sex), the denominator is the number of subjects in that subgroup/treatment group/analysis set. For most safety tables the study teams should use the default statistics; the study team should carefully consider and give sufficient justification prior to requesting the use of other summary statistics. Percentages will be reported to 1 decimal place, except when the percentage equals exactly 100 where it will be displayed as an integer (100). For zero, only count and no percentage will be

Document: \\quintiles.net\Enterprise\Apps\sasdata\SASa\sas\Shire\Teduglutide\ZXA48914\Biostatistics\Documentation\Protocol\SHP633-303\_Retrospective\_SAP\_Final\_V1.0\_20171013  
Author: [REDACTED] Version Number: Final V1.0  
Version Date: 13Oct2017

Template No: CS\_TP\_BS016 – Revision 3  
Effective Date: 01May2012

Reference: CS\_WI\_BS005

Copyright © 2012 Quintiles Transnational Corp. All rights reserved.  
The contents of this document are confidential and proprietary to Quintiles Transnational Corp. Unauthorized use, disclosure or reproduction is strictly prohibited.

displayed.

- **ALIGNMENT**

Output should be aligned so that in the body of the table, where applicable, text is left-justified within a cell, stats output is aligned centrally within a cell and lined up by decimal point.

Handling of missing values: In listings, missing values for numerical data will be reported as a period “.” and missing values for character data as a blank “ ”. In the summary tables for categorical data, “Missing” will always be displayed as a category to represent missing data, where applicable. The default denominator will be all subjects in the analysis set unless otherwise specified in the SAP. For both tables and listings where there are no observations (and hence there would be no output), the table/listing should be produced with all titles and footnotes as per its shell, but with the text showing no observations in the body of the output.

- **DECIMAL PLACES AND ROUNDING RULES**

- For measures of median and mean, use 1 decimal place beyond those used for the measurement.
- For measures of standard deviation and standard error, use 2 decimal places beyond those used for the measurement.
- For measures of minimum and maximum values, use the same number of decimal places as those used for the measurement.
- $\geq 5$  is rounded up away from zero, whereas  $<5$  is rounded down toward zero to account for rounding of negative numbers.
- BMI should be rounded to 1 decimal place for reporting.
- Derived questionnaire scores, and other similar efficacy parameters recorded as integers, should be rounded to 1 decimal place for reporting.

- **PRESENTATION OF TREATMENT GROUPS**

Tables will present TED/NTT, TED/TED, and ANY TED. The subjects will be grouped based on the treatment they received in the core study TED-C13-003 (teduglutide exposed) and retrospective period (teduglutide exposed and non-exposed). If the number of treatment

Document: \\quintiles.net\Enterprise\Apps\sasdata\SASa\sas\Shire\Teduglutide\ZXA48914\Biostatistics\Documentation\Protocol\SHP633-303\_Retrospective\_SAP\_Final\_V1.0\_20171013  
Author: [REDACTED] Version Number: Final V1.0  
Version Date: 13Oct2017

Template No: CS\_TP\_BS016 – Revision 3  
Effective Date: 01May2012

Reference: CS\_WI\_BS005

Copyright © 2012 Quintiles Transnational Corp. All rights reserved.  
The contents of this document are confidential and proprietary to Quintiles Transnational Corp. Unauthorized use, disclosure or reproduction is strictly prohibited.

groups dictates that not all can fit on 1 page, then, unless specified in the corresponding "General considerations", it will be left to the discretion of the shell author, following discussions with study team, as to how these will be presented. For example, some of the treatment groups may be presented in a separate table. If presenting subgroups, Shire recommends that sub-headers are added so that a tabulation is repeated by subgroup (rather than adding extra columns in the table to show the subgroups). These should be ordered per the CRF decode e.g. 1=Male, 2=Female.

## APPENDIX 2. TABLE, FIGURE AND DATA LISTING SHELLS

### TABLE AND FIGURE SHELLS

See separate file.

### DATA LISTING SHELLS

See separate file.

---

Document: \\quintiles.net\Enterprise\Apps\sasdata\SASa\sas\Shire\Teduglutide\ZXA48914\Biostatistics\Documentation\Protocol\SHP633-303\_Retrospective\_SAP\_Final\_V1.0\_20171013  
Author: [REDACTED] Version Number: Final V1.0  
Version Date: 13Oct2017

Template No: CS\_TP\_BS016 – Revision 3  
Effective Date: 01May2012

Reference: CS\_WI\_BS005

Copyright © 2012 Quintiles Transnational Corp. All rights reserved.  
The contents of this document are confidential and proprietary to Quintiles Transnational Corp. Unauthorized use, disclosure or reproduction is strictly prohibited.

## MODIFICATION HISTORY

Unique Identifier for this Version	Date of the Document Version	Author	Significant Changes from Previous Authorized Version
Draft 1.0	23OCT2017	[REDACTED]	Not Applicable – First Version
Draft 1.1	12Dec2017	[REDACTED]	General edits
Draft 1.2	16Jan2018	[REDACTED]	General Edits

Document: \\quintiles.net\Enterprise\Apps\sasdata\SASa\sas\Shire\Teduglutide\ZXA48914\Biostatistics\Documentation\SAP\SHP633-303\_SAP\_Draft\_V1.0\_20171023

Author: [REDACTED] Version Number: Draft V1.2  
Version Date: 16Jan2018

Template No: CS\_TP\_BS016 – Revision 3  
Effective Date: 01May2012

Reference: CS\_WI\_BS005

Copyright © 2012 Quintiles Transnational Corp. All rights reserved.  
The contents of this document are confidential and proprietary to Quintiles Transnational Corp. Unauthorized use, disclosure or reproduction is strictly prohibited.

## 1. LIST OF ABBREVIATIONS

AE	Adverse Event
AESI	Adverse Events of Special Interest
ALT	Alanine Aminotransferase
AST	Aspartate Aminotransferase
BMI	Body Mass Index
CDC	Centers for Disease Control and Prevention
CSR	Clinical Statistical Report
CTMS	Clinical Trial Management System
CxDy	Cycle x Day y
eCRF	Electronic Case Report Form
EOS	End of Study
ET	Early Termination
FOBT	Fecal Occult Blood Testing
FOCBP	Females of Childbearing Potential
GFR	Glomerular Filtration Rate
GGT	Gamma Glutamyl Transferase
HRQoL	Health-Related Quality of Life
ICF	Informed Consent Form
INR	Prothrombin International Normalized Ratio
IVRS	Interactive Voice Response System
LLQ	Lower Limit of Quantification
MedDRA	Medical Dictionary for Regulatory Activities
NTT	No-Teduglutide Treatment
NTx	No-Teduglutide Period x
PedsQL	Pediatric Quality of Life
PS	Parenteral Support
PT	Preferred Term
Px	Pre-Treatment Visit x
QD	Once Daily
SAE	Serious Adverse Event
SAP	Statistical Analysis Plan
SBs	Short Bowel Syndrome
SC	Subcutaneous
SOC	System Organ Class
SRN	All Subjects Screened
TEAE	Treatment-Emergent Adverse Event
TESAE	Treatment-Emergent Serious Adverse Event
TFLs	Tables, Figures and Listings
ULQ	Upper Limit of Quantification
WHODD	Who Drug Dictionary

Document: \\quintiles.net\Enterprise\Apps\sasdata\SASa\sas\Shire\Teduglutide\ZXA48914\Biostatistics\Documentation\SAP\SHP633-303\_SAP\_Draft\_V1.0\_20171023

Author: [REDACTED]

Version Number:

Draft V1.2

Version Date:

16Jan2018

Template No: CS\_TP\_BS016 – Revision 3

Effective Date: 01May2012

Reference: CS\_WI\_BS005

Copyright © 2012 Quintiles Transnational Corp. All rights reserved.

The contents of this document are confidential and proprietary to Quintiles Transnational Corp. Unauthorized use, disclosure or reproduction is strictly prohibited.

## 2. INTRODUCTION

This document describes the rules and conventions to be used in the presentation and analysis of prospective data for Protocol SHP633-303. It describes the data to be summarized and analyzed, including specifics of the statistical analyses to be performed.

This statistical analysis plan (SAP) is based on protocol amendment 2, dated 17 March 2017.

## 3. STUDY OBJECTIVES

### 3.1. PRIMARY OBJECTIVE

The primary objective of the study is to evaluate the long-term safety and tolerability of teduglutide treatment in pediatric subjects with Short Bowel Syndrome (SBS) who completed TED-C13-003.

### 3.2. SECONDARY OBJECTIVE

The secondary objective of the study is to evaluate the long-term efficacy of teduglutide treatment in pediatric subjects with SBS who completed TED-C13-003.

## 4. STUDY DESIGN

### 4.1. GENERAL DESCRIPTION

This is a Phase 3, retrospective and prospective, open-label, long-term extension study to evaluate the safety and efficacy of teduglutide in pediatric subjects who completed the TED-C13-003 study (the core study). At the time of entry into the TED-C13-003 study, subjects were less than 18 years of age, were dependent on parenteral nutrition to provide at least 30% of their caloric or fluid needs, and had not been able to significantly reduce parenteral support (PS) for at least 3 months prior to enrollment. During the core study, pediatric subjects were entered into one of three teduglutide dosing cohorts: 0.0125 mg/kg/day, 0.025 mg/kg/day, or 0.05 mg/kg/day, based on the timing of their enrollment in the study, or a standard of care SOC cohort. The teduglutide dosing cohorts were filled in a sequential manner.

Document: \\quintiles.net\Enterprise\Apps\sasdata\SASa\sas\Shire\Teduglutide\ZXA48914\Biostatistics\Documentation\SAP\SHP633-303\_SAP\_Draft\_V1.0\_20171023

Author: [REDACTED]

Version Number:

Draft V1.2

Version Date:

16Jan2018

Template No: CS\_TP\_BS016 – Revision 3

Reference: CS\_WI\_BS005

Effective Date: 01May2012

Copyright © 2012 Quintiles Transnational Corp. All rights reserved.

The contents of this document are confidential and proprietary to Quintiles Transnational Corp. Unauthorized use, disclosure or reproduction is strictly prohibited.

Approximately 40 subjects who completed the core study are expected to enroll in this extension study (SHP633-303). When signing the informed consent form (ICF) for this study, subjects can choose to participate in both retrospective and prospective portions of the study or only retrospective data collection. After informed consent/assent is obtained, study eligibility will be assessed for all subjects.

Subjects who previously received teduglutide during TED-C13-003, as well as subjects who were in the standard of care treatment group, may be eligible to receive repeat doses of teduglutide 0.05 mg/kg subcutaneous (SC) once daily injection in this extension study. Subjects not receiving teduglutide treatment (i.e., in a no-teduglutide treatment [NTT] period), will be seen approximately every 12 weeks for safety, PS requirements, and quality of life. The first NTx visit following the screening visit should occur within 2 to 12 weeks of screening. At any point after screening or during a NTT period, subjects who meet at least one teduglutide treatment inclusion criteria, may proceed immediately to the pre-treatment visit if the investigator, subject, and parent agree to proceed with teduglutide therapy.

After the pre-treatment visit, subjects who meet at least one of the teduglutide treatment inclusion criteria, and meet none of the teduglutide treatment exclusion criteria, will start a 28-week cycle, consisting of 24 weeks of teduglutide treatment at 0.05 mg/kg SC once daily, followed by a 4-week follow-up period (during which no teduglutide is administered). During the 28-week cycle, clinic visits will occur at weeks 1, 2, 4, 6, 9, 12, 16, 20, 24, and 28. Phone visits are required approximately 1 week after adjustments in PS during the teduglutide treatment period (between weeks 1 and 24), and weekly during the teduglutide follow-up period (between weeks 24 and 28). Safety and PS requirements will be evaluated at every visit, and quality of life assessments will be made approximately every 12 weeks. If a subject has clinical deterioration and meets follow-up period escape criteria after stopping teduglutide, the subject may "escape" the follow-up period early and proceed immediately to another pre-treatment visit. Following completion of the 28-week treatment cycle, the subject will proceed to an NTT visit within approximately 12 weeks.

Document: \\quintiles.net\Enterprise\Apps\sasdata\SASa\sas\Shire\Teduglutide\ZXA48914\Biostatistics\Documentation\SAP\SHP633-303\_SAP\_Draft\_V1.0\_20171023

Author: [REDACTED]

Version Number:

Draft V1.2

Version Date:

16Jan2018

Template No: CS\_TP\_BS016 – Revision 3

Effective Date: 01May2012

Reference: CS\_WI\_BS005

Copyright © 2012 Quintiles Transnational Corp. All rights reserved.

**Table A: Study Design Flow Chart**

Figure legend: Safety and efficacy data for subjects not receiving teduglutide treatment are captured approximately every 12 weeks, but subjects may proceed to the pre-treatment visit at any time in order to assess eligibility for teduglutide therapy. Eligible subjects will enter a 28-week teduglutide cycle. During this cycle, subjects will return to the site for safety and efficacy assessments at weeks 1, 2, 4, 6, 9, 12, 16, 20, and 24 (**solid black lines**). Phone visits are required approximately 1 week after adjustments in PS during the intervening weeks between weeks 2 and 24 (**dashed grey lines**). Subjects discontinue teduglutide at week 24 and enter a 4-week follow-up (no-treatment) period, during which phone visits will be performed weekly (**solid grey lines**). If an escape criterion is met during the follow-up period, subjects may proceed directly to another pre-treatment visit.

## 4.2. SCHEDULE OF EVENTS

Schedule of events for prospective data collection can be found in Section 7.1 of the protocol.

## 4.3. CHANGES TO ANALYSIS FROM PROTOCOL

There is no change of analysis from the protocol.

## 5. PLANNED ANALYSES

The following analyses will be performed for this study:

- Interim Analysis of Prospective Data
- Final Analysis

Document: \\quintiles.net\Enterprise\Apps\sasdata\SASa\sas\Shire\Teduglutide\ZXA48914\Biostatistics\Documentation\SAP\SHP633-303\_SAP\_Draft\_V1.0\_20171023

Author: [REDACTED] Version Number: Draft V1.2  
Version Date: 16Jan2018

Template No: CS\_TP\_BS016 – Revision 3  
Effective Date: 01May2012

Reference: CS\_WI\_BS005

Copyright © 2012 Quintiles Transnational Corp. All rights reserved.  
The contents of this document are confidential and proprietary to Quintiles Transnational Corp. Unauthorized use, disclosure or reproduction is strictly prohibited.

## 5.1. INTERIM ANALYSIS OF PROSPECTIVE DATA

An interim analysis of prospective data is conducted to support the sNDA submission, the results of which will be based on the defined treatment groups (See Section 6).

Derivations and definitions for the interim analysis will be based on those required for the final analysis contained in this analysis plan, unless deviations are stated within the text. The list of outputs provided with the full set of output templates (planned for the final analysis) will highlight which of these outputs will also be provided for the interim analysis.

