## 7.7. COMMON CALCULATIONS

For quantitative measurements, change from baseline will be calculated as:

Test Value at Visit X – Baseline Value

Percent change from baseline will be calculated as:

(Test Value at Visit X – Baseline Value) / Baseline Value \*100

Change (or percent change) from baseline tables will be calculated based on the number of subjects in the treatment group with a non-missing value at baseline and at the time point being analyzed.

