### **8.3. MISSING DATA**

Missing data will in general not be imputed. However, partial dates will contribute to the analysis as described in Appendix 2. All available data will be included in the safety analysis.

Details for the imputation algorithm for the missing endpoint values for PS parameters (volume, calories and etc.) will be described in Section [16.1.1](#) of this analysis plan.

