## **10. DISPOSITION AND WITHDRAWALS**

All subjects who provide informed consent for prospective data collection in the extension study will be accounted for in the analyses. After signed consent (and informed assent, if applicable), a subject will be considered enrolled in the study if the subject meets all of the inclusion criteria at the screening. Teduglutide treatment eligibility does not impact study eligibility.

If the investigational product is discontinued prematurely during a teduglutide treatment cycle and the subject wishes to remain in the study, the evaluations listed for the EOT visit are to be performed. A 4-week follow-up period will ensue, consisting of weekly telephone visits (CxW25-27) and the week 28 clinic visit (CxW28). The subject would then enter a NTT period and could be evaluated for subsequent teduglutide treatment eligibility according to the study

Document:	\quintiles.net\Enterprise\Apps\sasdata\SASa\sas\Shire\Teduglutide\ZXA48914\Biostatistics\Documentation\SAP\SHP633-303_SAP_Draft_V1.0_20171023		
Author:	[REDACTED]	Version Number:	Draft V1.2

Template No: CS\_TP\_BS016 – Revision 3  
Effective Date: 01May2012

Reference: CS\_WI\_BS005

Version Date:  
16Jan2018

Copyright © 2012 Quintiles Transnational Corp. All rights reserved.  
The contents of this document are confidential and proprietary to Quintiles Transnational Corp. Unauthorized use, disclosure or reproduction is strictly prohibited.

schedules. The reason for permanent treatment discontinuation will be captured.

The reason(s) for permanent discontinuation of treatment and/or withdrawal from the study must be determined by the investigator, and recorded in the subject's medical record and in the electronic case report form (eCRF). If a subject is withdrawn for more than one reason, each reason should be documented in the source document, and the most clinically relevant reason should be entered in the eCRF. Overall reasons for discontinuation of treatment and withdrawal from study will be summarized separately based on the following categories:

- Adverse event
- Protocol deviation
- Lack of efficacy
- Physician decision
- Withdrawal by subject
- Withdrawal by parent/guardian
- Lost to follow-up
- Pregnancy
- Death
- Other

The ongoing subjects will be counted in the table for interim analysis.

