## 16. EFFICACY OUTCOMES

Efficacy endpoints for PS will be analyzed at the end of each teduglutide treatment cycle (Week 24 or EOT), and at each study visit, relative to the baseline of the core study (TED -C13-003). The efficacy analyses will be performed on PS diary data and PS prescribed data for safety population. The descriptive statistics of efficacy outcomes will be summarized by treatment group as defined in Section 6. The listings for efficacy measures which are collected on the CRF forms will be provided.

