#### 16.1.1.1. Reduction in PS volume

PS volume reduction at the end of each teduglutide treatment period (Week 24 or EOT) and at all other study scheduled visits compared to the baseline of the core study TED-C13-003 will be calculated using average daily values. The number and percentage of subjects who achieve at least a 20% reduction in PS volume (mg/kg/day) at the end of each teduglutide treatment period during the prospective observation period will be summarized. Similar analysis will be done for 50% and 75% reduction in PS volume. This parameter will be summarized for both actual and prescribed data.

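### At the interim, a pooled end-of-cycle PS summary would draw on cycles still in progress only through early stoppers, and no denominator is stated for its percentages

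*SAP*

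**What the plan says.** All references are to the prospective SAP (Draft V1.2).

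- **Purpose and rules of the interim (section 5.1).** "An interim analysis of prospective data is conducted to support the sNDA submission". On method, "Derivations and definitions for the interim analysis will be based on those required for the final analysis contained in this analysis plan", with exceptions only where the text states them. A separate list is to mark which outputs are run at the interim.
- **Time point (section 16).** "Efficacy endpoints for PS will be analyzed at the end of each teduglutide treatment cycle (Week 24 or EOT), and at each study visit". Sections 16.1.1.1 (20%, 50% and 75% reductions) and 16.1.1.3 (complete weaning) use the same end-of-period time point. Section 16.1.1.5 (hours and days by level of reduction) uses end of treatment within a cycle.
- **Early stopping (section 10).** When drug is stopped prematurely and the child stays in the study, "the evaluations listed for the EOT visit are to be performed". A record labelled EOT can therefore exist well before Week 24.
- **Missing values.** Section 8.3: "Missing data will in general not be imputed". Section 7.7 limits change summaries to subjects "with a non-missing value at baseline and at the time point being analyzed".
- **Ongoing subjects (section 10).** "The ongoing subjects will be counted in the table for interim analysis". This sentence belongs to disposition and gives no rule for efficacy.
- **By-visit tables (section 7.5).** An EOT that does not coincide with Week 24 gets its own visit row.
- **Denominator (Appendix 1).** Percentages default to N of the treatment group or analysis set, unless something else is stated or the number at the time point is provided. Section 16.1.1.1 states nothing else.

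**The concern.** The Week 24 or EOT rule works at the final analysis, when every cycle has ended one way or the other. At a data cut some cycles are open. From an open cycle, the only child who can already have an end-of-cycle value is one who has stopped. Entry to the pooled set from recent cycles is therefore conditional on early stopping.

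The figures at stake are the interim end-of-cycle percentages with at least 20%, 50% and 75% PS volume reduction, and the end-of-treatment changes in hours and days. They could differ between interim and final for a reason unrelated to the drug. The unstated denominator adds a second uncertainty: two programmers following the plan could report very different percentages from the same data.

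**Working it through.** The SAP gives no figure to reproduce here. The check is a count, followed by an illustration on declared assumptions.

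**Direction.** Let C cycles have a closed 24-week window at the cut, c of them ended early, and let x early stops come from open cycles. The share of early stoppers among available end-of-cycle records is (c + x)/(C + x), against c/C in closed cycles. The difference is x(C − c)/[C(C + x)], which is positive whenever x > 0 and c < C. No assumption about response is needed.

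**Worked count.** Section 4.1 expects about 40 subjects; take one cycle each, for scale only. Assume 20 closed cycles with 2 early stops, and 20 open cycles with 1 early stop so far and 19 children on drug. Assume 70% of completers and 30% of early stoppers respond.

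- Early-stopper share: 3/21 = 14.3%, against 2/20 = 10.0% in closed cycles.
- Response in closed cycles: (18 × 0.7 + 2 × 0.3)/20 = 66.0%.
- Response on available records: (18 × 0.7 + 3 × 0.3)/21 = 64.3%.
- Response over N = 40: (18 × 0.7 + 3 × 0.3)/40 = 33.8%.

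**Range.** Let f be the share of started cycles still open (assumed 0.2 to 0.8) and d the 24-week early-stop probability (assumed 0.05 to 0.20). With starts and stops spread evenly, half of the eventual early stops in open cycles have happened by the cut. Then

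s = [(1 − f)d + f·d/2] / [(1 − f) + f·d/2]

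is the early-stopper share on available records. The response rate shifts by −(response gap) × (s − d), with the gap taken as 40 points.

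| d | f | s | Response, closed cycles | Response, available records | Response, over N |
|---|---|---|---|---|---|
| 0.05 | 0.2 | 5.6% | 68.0% | 67.8% | 54.5% |
| 0.05 | 0.8 | 13.6% | 68.0% | 64.5% | 14.2% |
| 0.10 | 0.5 | 14.3% | 66.0% | 64.3% | 33.8% |
| 0.20 | 0.2 | 22.0% | 62.0% | 61.2% | 50.2% |
| 0.20 | 0.8 | 42.9% | 62.0% | 52.9% | 14.8% |

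On available records the shift runs from 0.2 points (68.0 − 67.8) to 9.1 points (62.0 − 52.9).

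**Sensitivity to the gap.** With a 50-point gap (70% against 20%), d = 0.15 and f = 0.5, s is 20.9% and response reads 59.5% instead of 62.5%. With f = 0.75, s is 30.6% and response reads 54.7%. With no gap, the rate on available records does not move.

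**What the restriction does.** If only closed cycles enter, the expected early-stopper share is d for every f.

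**The case against.** The strongest case against has five parts.

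1. **Unseen outputs.** The list of interim outputs and the table shells are separate files, so nothing shown confirms that any pooled end-of-cycle table is run at the interim. This stands, and the point is conditional on such a table being run. A reader might infer that the main efficacy figures of the submission are biased. The SAP does not support that: efficacy is the secondary objective (section 3.2), and section 16 also calls for analysis at each study visit.
2. **Section 7.5.** Because an off-schedule EOT has its own row, the Week 24 row of by-visit tables takes no early stopper from an open cycle, apart from an EOT inside the Week 24 window. This stands and confines the point to pooled summaries.
3. **Denominator.** Rates on available records are not necessarily what the plan would produce, since the default is N. This is correct, but it does not remove the problem. Under N, children still on drug are in the denominator and cannot be in the numerator. Appendix 1 also asks for a Missing category where applicable; that would disclose them but leave the percentage unchanged.
4. **Weaning.** Section 16.1.1.3 asks how many subjects wean, which is a count. Extra early stoppers cannot lower a count, so weaning should not be listed among the shifted rates.
5. **Size.** Every quantity behind the percentages is assumed. The discontinuation reasons in section 10 do not show that early stoppers respond less. The analysis is descriptive, and a downward shift would understate efficacy. All of this stands, and it limits how strongly the point can be put.

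**Conclusion.** The point holds for any pooled Week 24 or EOT summary of PS run at the interim under the final-analysis derivations. Over-representation of early stoppers among available records follows from the SAP's own definitions once one open cycle contains an early stop with an EOT record, provided at least one closed cycle was completed. No section removes it.

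The size cannot be fixed from the SAP. Under the assumptions shown, the response rate on available records falls by about 0.2 to 9 points, and only if early stoppers respond less than completers. That range is not a bound, since it depends on the stop rate, the open share and the gap chosen. Under the default N the fall is larger, because children still on drug count as not having responded.

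By-visit Week 24 rows and cycles closed before the cut are sound. This is an inexpensive correction to make before the interim, not evidence that the efficacy results as a whole are biased.

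**What to change.** Add to section 5.1 of the prospective SAP:

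- Interim end-of-cycle efficacy summaries include only cycles whose Day 1 is at least 24 weeks plus the 4-day Week 24 window of section 7.5 before the data cut (24 × 7 + 4 = 172 days), whether or not the child completed the cycle.
- Those cycles are the denominator for percentages.
- The number of cycles ongoing or started too recently is shown beside each such table, and any early EOT values from them are listed.

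By-visit summaries stay as they are. The cost is a few sentences and a date filter. The downside is that a few observed early EOT values appear only in a listing until the final analysis. Showing the number ongoing without the restriction would disclose the selection, but it would leave the percentage distorted and the denominator open.
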